## 18. Economics Analyses

We will conduct full economic evaluations (cost-utility and cost-effectiveness analyses) of SA and EA compared to UMC according to Medicare (payer) and health care sector perspectives and following economic evaluation best practices . These full analyses will be conducted for the Kaiser Permanente and Sutter Health clinical sites where the capture of all health care utilization is available through administrative data from the Health Care Systems Research Network Virtual Data Warehouse (HCSRN VDW). Unfortunately, IFH is not a member of this VDW and only provides primary care. However, as we perform these analyses, we will explore how to capture some comparable usage and cost data for IFH.

The cost-utility analyses will use gains quality-adjusted life-years (QALYs) measured using the EQ-5D-5L  across the year to calculate QALYs following an area under the curve approach correcting for baseline . The cost-effectiveness analyses will use the proportion of participants in each group who experienced at 12 months MCID (30%) reduction in the RMDQ from baseline.

Costs to be collected. Medical care utilization and intervention costs will be considered. Medical care utilization includes pharmacy, outpatient visits (including specialty care), inpatient stays, and referrals and will be captured from the VDW. For the Medicare perspective this health care utilization, whether provided within Medicare Advantage programs, Medicare fee for service programs or other health plans for those still on their employers' plans, will be valued using standard costing algorithms and Medicare fee schedules. For the health care sector perspective, we will add in estimates of patients' out-of-pocket (e.g., copay) amounts by cost category. The cost of the intervention (acupuncture) will be captured from study records (number of acupuncture treatment sessions received) and valued using typical community rates. For the Medicare perspective we will analyze different assumptions for the amount reimbursed by Medicare.

Cost-effectiveness calculations. We will aggregate and calculate the incremental average cost per participant in each treatment arm (SA and EA) compared to UMC ( $C_{SA} - C_{UMC}$  and  $C_{EA} - C_{UMC}$ ) and compare those incremental costs to incremental benefits between groups in terms of QALYs gained and additional patients who saw at least a MCID reduction in RMDQ. If costs of either of the acupuncture arms compared to UMC are reduced and effectiveness increased it will be said to be cost saving and to dominate UMC in terms of cost effectiveness . If incremental costs and effectiveness are both increased then an incremental cost-effectiveness ratio will be calculated and compared to society's willingness-to-pay for an additional QALY (often \$50,000 to \$100,000 per QALY is used)  to see if it can be considered cost-effective.

Because acupuncture may influence other common CLBP comorbidities (e.g., depression and sleep) we will capture both total healthcare utilization for our base case and back-pain-related-only utilization to be included in a sensitivity analysis. We will calculate overall cost-effectiveness as well as the cost-effectiveness by site so that we can examine differences in healthcare utilization and its changes across sites. All cost effectiveness analyses will follow intention to treat.

A bootstrap methodology will be used to estimate confidence intervals,  as well as to produce cost-effectiveness planes and cost-effectiveness acceptability curves to show variation around our results . One-way sensitivity analyses will be performed to determine the robustness of our estimates with different assumptions such as the reimbursement rate for acupuncture and the inclusion of only back-related costs .

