Measures of both costs and effectiveness are needed for cost-effectiveness analysis. We will use the EQ-5D, one of the most commonly used measures of generic health status, to generate our measures of effectiveness. It measures five dimensions of health status (mobility, self-care, usual activities, pain and discomfort, anxiety and depression) and has five levels for each of these (having no problems to having extreme problems). Scores on each of these dimensions are then weighted using US population preference weights⁹⁰ to generate a time point-specific

measure of health-related quality of life or utility. These utility values across the study period are used to calculate quality-adjusted life-years (QALYs), a generic measure of health improvement.

We will be calculating cost-effectiveness from both a health care sector and a Medicare perspective. The health care sector perspective includes all “formal health care sector (medical) costs borne by third-party payers.”⁹¹ The Medicare perspective includes all costs Medicare would likely reimburse. Because there is no efficient and timely way to capture non-Medicare-reimbursed costs for the SH and IFH health systems, we will only calculate the health care sector perspective for participants in the Kaiser systems. Measures of *health care utilization* within the health care system (provider visits, imaging studies, prescription medications, costs) will be captured from the electronic health record and/or from Medicare claims data. We will identify and separately include back pain-related costs in our analyses. The use of acupuncture sessions will be captured from study records.

Aim 3 qualitative data collection:

The qualitative work on this study focuses on both formative and summative evaluation questions.⁹² The evaluation will use the RE-AIM (reach, effectiveness, adoption, implementation, maintenance) model.^{94,95} After the clinical trial is well underway (UH3 year 2), we will conduct interviews and/or virtual focus groups with patients (and potentially with acupuncturists) who have participated in the trial to get input on the implementation of the acupuncture interventions and document the experiences of participating patients (and potentially acupuncturists). Feedback from study acupuncturists may also be solicited through surveys.

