months of maintenance acupuncture (EA) in older adults with cLBP. Costs for the health care sector perspective will include the costs of all healthcare utilization priced using Medicare's national fee for service rates, including acupuncture visits, and costs from the payer perspective will only include the Medicare covered amounts, including the reimbursed costs of acupuncture.^{106,107} Effectiveness will be measured using quality-adjusted life-years (QALYs) based on changes (net of baseline)¹⁰⁸ in the preference-weighted⁹⁰ values of the EQ-5D¹⁰⁹ over the study year.

If costs of either of the acupuncture arms compared to UMC are reduced and effectiveness increased, we will describe acupuncture as cost saving and to dominate UMC in terms of cost effectiveness.¹⁰⁶ If incremental costs and effectiveness are both increased then an incremental cost-effectiveness ratio will be calculated and compared to society's willingness to pay for an additional QALY (\$50,000 to \$100,000 per QALY¹¹⁰) to see if acupuncture can be considered cost-effective.

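### Protocol and SAP build the two cost perspectives incompatibly; unless the SAP's fee-schedule values are net of cost sharing, the patient share is charged to Medicare and counted twice in the sector total

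*SAP*

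**What the plan says.** Three places define the perspectives, and they differ.

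- **Protocol 9.6 (Aim 2), with 9.5.4.** "Costs for the health care sector perspective will include the costs of all healthcare utilization priced using" Medicare's national fee-for-service rates, whereas "costs from the payer perspective will only include the Medicare covered amounts, including the reimbursed costs of acupuncture". Section 9.5.4 says the same in other words: the payer cost is the part of the sector cost that Medicare reimburses.
- **SAP 18.** "For the Medicare perspective this health care utilization, whether provided within Medicare Advantage programs, Medicare fee for service programs or other health plans", is valued with costing algorithms and the Medicare fee schedules. The next sentence reads: "For the health care sector perspective, we will add in estimates of" what patients pay out of pocket, by cost category. The fee-schedule value is thus the Medicare cost, and the sector cost is that value plus out-of-pocket amounts.
- **Protocol 6.2.2 (Aim 2 measures).** The sector perspective covers medical "costs borne by third-party payers", which leaves out the patient's own payments. The Medicare perspective covers what Medicare would be likely to reimburse.

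Study acupuncture is handled separately. SAP 18 takes the session count from study records, "valued using typical community rates", and continues: "For the Medicare perspective we will analyze different assumptions for the amount reimbursed by Medicare". Protocol 5.1 states that neither patients nor their insurers are billed for study visits.

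**The concern.** The same quantity, utilisation priced at Medicare rates, is the sector total in one document and the Medicare cost in the other. An analyst cannot follow both. The protocol reaches the payer cost by taking a part of that quantity; the SAP reaches the sector cost by adding to it. SAP 18 also has no step that reduces care other than acupuncture to the amount Medicare reimburses.

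If the fee-schedule value already contains the patient's share, the SAP's rule leaves that share in the Medicare cost and then adds it again for the sector. Both perspectives feed the comparison with $50,000 to $100,000 per QALY, and the protocol's rationale presents the trial as evidence for Medicare coverage. Neither sensitivity analysis named in SAP 18 (acupuncture reimbursement rate; back-related costs only) tests the patient share on other care. Bootstrap intervals describe sampling variation and cannot reveal a definitional error.

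**Working it through.** The plan gives no cost figure to reproduce, so the check is an accounting identity.

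**Inputs**
- F: value of medical care other than study acupuncture at Medicare rates, indexed at 100.
- s: patient share of that price. The documents give no value. It is assumed here over 5–30%, with 10–20% as the working range, and taken as equal across arms.
- Non-covered items are left out of the arithmetic, so the Medicare figures reflect cost sharing only.

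**Formulas for the cost level**
- Protocol 9.5.4/9.6: sector = F; Medicare = F(1 − s).
- SAP 18, values gross of the patient share: Medicare = F; sector = F + sF = F(1 + s).
- SAP 18, values net of the patient share: Medicare = F(1 − s); sector = F(1 − s) + sF = F.

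On the gross reading the sector excess is F(1 + s)/F − 1 = s, and the Medicare excess is F/[F(1 − s)] − 1 = 1/(1 − s) − 1.

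| Assumed s | Protocol: Medicare / sector | SAP gross: Medicare / sector | Medicare excess | Sector excess |
|---|---|---|---|---|
| 5% | 95 / 100 | 100 / 105 | 5.3% | 5% |
| 10% | 90 / 100 | 100 / 110 | 11.1% | 10% |
| 20% | 80 / 100 | 100 / 120 | 25.0% | 20% |
| 30% | 70 / 100 | 100 / 130 | 42.9% | 30% |

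In the 20% row, the SAP sector cost exceeds the protocol's Medicare cost by 120 − 80 = 40, which is twice the patient share of 20. On the net reading the SAP gives 80 and 100, exactly the protocol's figures.

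**Incremental cost**

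The ratio uses differences between arms, not levels. Let A be the study acupuncture cost, which the add-on does not touch, and D the difference in other care cost, acupuncture arm minus usual care.
- Protocol sector increment: A + D.
- SAP gross sector increment: A + D(1 + s).
- Distortion: sD.

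The Medicare increment shifts by the same amount: D − D(1 − s) = sD.

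For an assumed s = 20%, D = −$500, $0 or +$500 gives a shift of −$100, $0 or +$100. For s = 10% the shifts are −$50, $0 and +$50.

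**Which reading the text favours**
1. The protocol treats the reimbursed amount as a part of utilisation at Medicare rates. That makes sense only if the price includes something Medicare does not pay.
2. SAP 18 applies one valuation to Medicare Advantage, fee-for-service and employer-plan care alike. That looks like a price standard rather than amounts Medicare paid.
3. The SAP sentence on reimbursement assumptions follows directly on the acupuncture cost, and Protocol 9.6 ties such assumptions to acupuncture. They do not appear to reduce other care to its reimbursed part.

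These points favour the gross reading but do not prove it.

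**The case against.** The strongest reply is that double counting is inferred, not stated. SAP 18 never calls its values full or gross. They come partly from cited costing algorithms that the documents do not describe. Protocol 6.2.2 gives the net reading some support: it defines the Medicare perspective by what Medicare would reimburse, and it confines the sector analysis to the Kaiser systems because costs that Medicare does not reimburse are hard to capture elsewhere. That treats the sector as reimbursed plus unreimbursed costs, which is how SAP 18 is built. If the values are net, the add-on is correct. This stands, and it makes the double count conditional. It does not remove the conflict with Protocol 9.5.4 and 9.6, because the SAP does not say which basis it uses.

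It is also fair to say that the third-party-payer phrase in Protocol 6.2.2 is quoted there from a cited recommendation. It is a reason to align the text, not evidence of double counting.

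A reader might infer that both perspectives' cost-effectiveness ratios are overstated and could be pushed across the willingness-to-pay threshold. The documents do not support that. The distortion is sD: it is zero if other care costs the same in both arms, and it flatters acupuncture if acupuncture reduces other care. Study acupuncture is priced separately and not billed to patients, so the add-on does not scale it. The documents give no value for s, for D or for any expected ratio.

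**Conclusion.** The inconsistency is established: the two perspectives have incompatible definitions in Protocol 9.5.4/9.6, Protocol 6.2.2 and SAP 18. The double count is the more plausible result of following SAP 18 literally, but it depends on the fee-schedule values being gross of the patient share.

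On that condition, and for an assumed share of 10–20% of price, the level of medical care cost is too high by 10–20% for the sector and by 11–25% for Medicare. Incremental cost is distorted by the patient share times the between-arm difference in non-study care, with either sign. If the values are net, SAP 18 reproduces the protocol's totals and only the wording needs repair.

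The point affects Aim 2 only. It should be settled before costs are computed.

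**What to change.** Use the Protocol 9.5.4/9.6 definitions in SAP 18:

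- **Sector cost:** all utilisation at Medicare rates, with the patient share counted once. Add no out-of-pocket amount to values that already contain it.
- **Medicare cost:** the reimbursed portion only. From gross values, subtract patient cost sharing and non-covered items.
- **Basis:** state in SAP 18 whether the costing-algorithm and fee-schedule values are gross or net of cost sharing. If they are net, keep the add-on for the sector and subtract nothing for Medicare.
- **Protocol 6.2.2:** align the sector definition with the same text, so that it no longer stops at third-party payments.

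The cost is wording in two documents. The copay estimates already planned serve on either basis: they are subtracted for Medicare if the values are gross, or added for the sector if net. The one extra step, on the gross basis, is to identify non-covered items, which SAP 18 does not yet describe.

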The collected information will allow us to fully characterize acupuncture treatment practices and may provide important information for secondary exploratory analyses examining patient responsiveness to treatment. We have developed and used similar treatment visit forms for other studies,⁵⁷⁻⁵⁹ and have worked with our acupuncture advisory group during the UG3 year to refine these data collection forms and processes for the study. Minor changes were made after the pilot studies were completed. A copy of the acupuncture visit form is shown in Appendix 2.

Trial acupuncturists' fidelity to agreed upon practice parameters will be routinely and systematically assessed via their completion of the online, standardized study forms for each treatment session.

Any acupuncture care participants may seek independent of the study would be subject to usual care billing and documentation. However, no patients nor patient insurance policies will be billed for study-related visits, as consistent with other pragmatic trials conducted in the participating health systems.

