We will assess adherence by several means: attendance at acupuncture visits and the content of those visits. Because different participants might require different numbers of visits, we will ask the acupuncturists at each visit to let us know whether the patient is continuing treatment, has completed treatment or is unlikely to improve (including before and after at least 8 treatments as recommended by the Acupuncture Advisory Panel). This will allow us to determine whether a patient stops treatment prematurely. Even patients who stop the treatment prematurely in the standard treatment period but are randomized to receive maintenance acupuncture will be encouraged to make acupuncture visits in the maintenance period. We will assess acupuncturists' fidelity to the treatment protocol by reviewing completed treatment forms at the end of each treatment session, which will include key details of their study visit, the structure of the visit, needling details and acupuncture points used, visit duration, and self-care recommendations (Appendix 2 has a copy of the form). We will also ask patients about their use of non-study acupuncture treatments to characterize any acupuncture received by participants outside study provided services.

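### In the health care sector perspective, SAP 18 has no source or price for non-study acupuncture that participants pay for entirely themselves, and it prices plan-billed non-study sessions differently from study sessions

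*SAP*

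**What the plan says.** SAP 18 builds costs from two streams. For acupuncture: "The cost of the intervention (acupuncture) will be captured from study records (number of acupuncture treatment sessions received) and valued using typical community rates". Other care has its own sentence: "Medical care utilization includes pharmacy, outpatient visits (including specialty care), inpatient stays, and referrals and will be captured from the VDW". The Aim 2 measures in Protocol 6.2.2 agree on the first stream: "The use of acupuncture sessions will be captured from study records".

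SAP 18 values VDW care with costing algorithms and Medicare fee schedules, then widens one perspective: "For the health care sector perspective, we will add in estimates of patients' out-of-pocket (e.g., copay) amounts by cost category". Protocol 9.6 says that sector costs "will include the costs of all healthcare utilization priced using Medicare's national fee for service rates, including acupuncture visits". A little further on, the same section values study acupuncture at community rates.

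On acupuncture outside the study, Protocol 5.1 says: "Any acupuncture care participants may seek independent of the study would be subject to usual care billing and documentation". Protocol 5.3.1 allows every group whatever care they choose to buy, and 5.3.3 asks only the usual medical care (UMC) group to avoid acupuncture. Protocol 5.4 adds: "We will also ask patients about their use of non-study acupuncture treatments to characterize any acupuncture received by participants outside study provided services". The measures table in Protocol 6.2.2 marks the acupuncture-use item as asked at 12 months only, and lists patient report among the sources for utilization and costs. SAP 18 does not draw on that item.

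On the analysis principle, SAP 18 says: "All cost effectiveness analyses will follow intention to treat".

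**The concern.** Outside use is foreseeable. Protocol 9.2 and SAP 4 both give a UMC participant seeking acupuncture elsewhere as their example of crossover. Study treatment ends at about 3 months in the standard arm (SA) and 6 months in the enhanced arm (EA), while QALYs and the RMDQ responder measure run to 12 months. SA and EA participants therefore have 9 and 6 months in which they may go on at their own expense.

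Any effect of such sessions enters the EQ-5D and RMDQ results of the arm. If the participant pays in full, no cost need enter. The item left out is the service that the ratio is meant to value. The one-way sensitivity analyses that SAP 18 names (reimbursement rate, back-related costs only) do not reach it.

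There is also a pricing question. The same needling session carries one price if the study supplies it and may carry another if a plan is billed for it.

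**Working it through.** **Step 1. Follow each kind of session through SAP 18, health care sector perspective.**

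| Session | Cost stream | Price |
|---|---|---|
| Study session | Study records | Typical community rate |
| Non-study, billed to a plan | VDW, as far as it captures it | Costing algorithms and Medicare fee schedules, plus estimated out-of-pocket amounts |
| Non-study, paid entirely by the participant | None named | None named |

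The out-of-pocket line does not fill the third row. It adds estimated amounts by cost category, with copay as its example, and gives no means of finding a visit that was never recorded.

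**Step 2. How complete is the VDW row?** SAP 18 says all utilization can be captured at the Kaiser and Sutter sites. Protocol 6.2.2 says costs that Medicare does not reimburse cannot be obtained in a practical and timely way at Sutter or IFH, and so confines the sector perspective to Kaiser. By the Protocol 4.3.1.1 targets, Sutter is 204 of 288 + 174 + 204 = 666 participants at the SAP 18 sites, or 204/666 = 31%.

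**Step 3. Size.** The documents give no rate of outside use, session count, session price or expected QALY difference, so there is no plan figure to reproduce. Every input below is assumed.

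- Omitted cost per participant in an arm = share using outside acupuncture × sessions × price × (1 − share captured).
- Error in incremental cost = omitted cost in UMC − omitted cost in the acupuncture arm.
- Error in the ratio = error in incremental cost ÷ QALY difference.

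With 8 sessions at $75, none captured, and a QALY difference of 0.03:

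| UMC use | Acupuncture arm use | Error in incremental cost | Error per QALY |
|---|---|---|---|
| 20% | 0% | 0.20 × 8 × 75 − 0 = +$120 | 120/0.03 = +$4,000 |
| 20% | 10% | 120 − 60 = +$60 | +$2,000 |
| 10% | 10% | 60 − 60 = $0 | $0 |
| 5% | 20% | 30 − 120 = −$90 | −$3,000 |

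Against the $50,000 to $100,000 per QALY that SAP 18 cites, $4,000 is 8% to 4%.

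For a wider range in one arm, take 5% to 30% of participants, 5 to 15 sessions and $50 to $100 each. The gross omission runs from 0.05 × 5 × 50 = $12.50 to 0.30 × 15 × 100 = $450 per participant with no capture. It is half that ($6.25 to $225) with half captured, and $0 with full capture. The extreme corner, $450 omitted in UMC and none in the other arm, gives 450/0.03 = $15,000 per QALY, or 450/0.01 = $45,000 if the QALY difference is only 0.01.

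**The case against.** The best defence is that the gap is narrow. The study-records sentence concerns the intervention, and care outside the study goes through usual billing (Protocol 5.1) and so into the VDW. Protocol 6.2.2 defines the sector perspective as costs borne by third-party payers, under which self-paid sessions are out by definition. UMC is asked not to use acupuncture. The patient item comes once, at 12 months, and the documents do not show that it records session counts, dates or payer. All this belongs to a secondary aim.

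Much of that stands, and it rules out several stronger readings that a reader might infer:

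- That no acupuncture outside the study is costed. Plan-billed sessions belong to the VDW stream.
- That effects follow intention to treat while costs do not. SAP 18 applies the principle to all cost-effectiveness analyses, costs included. The weakness is incomplete capture of one cost.
- That the Medicare perspective is also wrong. It covers what Medicare would likely reimburse, so self-paid sessions are rightly left out.
- That the omissions cannot cancel because only UMC is asked to abstain. That request may lower UMC use, but UMC also receives no study sessions, which may raise it. Equal use gives zero error.

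The third-party-payer argument does not close the matter. SAP 18 adds out-of-pocket amounts to the sector perspective, and once they are in, leaving out a fully self-paid session while counting a copay needs a reason that the plan does not give.

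**Conclusion.** The point holds for one perspective and mainly one kind of session. In the health care sector perspective, fully self-paid non-study acupuncture is in neither cost stream, although patient report is collected on it. Plan-billed sessions are covered as far as the VDW captures them, which the Protocol doubts at Sutter for care that Medicare does not reimburse, and they are priced on a different basis from study sessions.

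The error in incremental cost is the difference between arms in uncaptured sessions. The documents support neither a sign nor a size. UMC use makes acupuncture look less cost-effective than it is, and SA or EA use makes it look more so. The $120, or $4,000 per QALY, illustrates a one-sided case and rests wholly on assumed inputs. Aim 1 is unaffected. This is a worthwhile, inexpensive improvement to Aim 2.

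**What to change.** In SAP 18, for the health care sector perspective:

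1. Count acupuncture in every arm as study sessions plus non-study sessions. Take non-study sessions from the VDW where billed and otherwise from the 12-month patient report, with a rule against counting any session twice.
2. Use one unit price for all acupuncture sessions, reconciling the community rate in SAP 18 with the Medicare rate in Protocol 9.6.
3. If the patient report holds no session count, state an assumed count and a range.
4. Report study plus VDW sessions only as a one-way sensitivity analysis.

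Leave self-paid sessions out of the Medicare perspective.

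Also reconcile the two definitions of the sector perspective: Protocol 6.2.2 has third-party-payer costs at Kaiser only, while SAP 18 adds out-of-pocket amounts and includes Sutter.

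The cost is SAP wording and a derived variable based on an item already in the measures table. The downside is recall error over up to 12 months, and reliance on an assumed count if the item records only whether acupuncture was used.

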3. STUDY DESIGN

We propose a three-arm multi-site parallel design, pragmatic trial with 789 participants to evaluate the effectiveness of two groups of acupuncture to improve functional outcomes (primary outcome), and pain intensity and pain interference (key secondary outcomes) of older adults (≥ 65 years) with cLBP. We will compare SA (3 months of acupuncture, with up to 15 visits) and EA (3 months of SA, 3 months maintenance acupuncture with up to 6 visits) to UMC (each group, N=263). Participants will be recruited from four healthcare systems (HCSs): Kaiser Permanente Washington - KPWA and Kaiser Permanente Northern California - KPNC, which have Kaiser Permanente integrated health plans; Sutter Health- SH, a largely fee for service organization; and the Institute for Family Health - IFH, a network of federally-qualified health centers (FQHCs). Study participants will be individually randomized with randomization stratified by HCS, age, and gender. The primary outcome will be back-related disability, measured by the Roland Morris Disability Questionnaire (RMDQ) with a primary time point of 6 months. Key secondary outcomes include pain interference and pain intensity and back-related disability outcomes at 3 and 12-months. Thus, we will be able to assess the value of both a course of standard acupuncture (up to 15 sessions over 3 months of treatment) and of the addition of

maintenance acupuncture (up to 6 additional treatment sessions over months 4-6) for improving outcomes. We will include some pre-planned subgroup analyses to shed light on groups that may particularly benefit from acupuncture and those that do not. We will also conduct a cost-effectiveness analysis of both types of acupuncture compared to UMC and a formative and summative analysis to help us understand important facilitators and barriers for broader scale implementation of acupuncture – should it prove useful.

Participants will remain in the trial for 12 months and we anticipate the duration of enrollment and follow-up to be 29 months. We anticipate that acupuncture will be administered in outpatient clinics within participating HCSs and acupuncturist's offices in the community.

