##### Secondary Objectives

To examine the effectiveness of acupuncture at 3 and 12 months for improving back-related disability and to evaluate additional outcomes, including the PEG, a 3-item composite measure of pain intensity and pain interference with enjoyment of life and with general activity at 3, 6 and 12 months.

**Aim 2:** To conduct a cost-effectiveness analysis of enhanced acupuncture and standard acupuncture compared to usual care.

**Aim 3:** To conduct formative and summative evaluations to understand, describe and explain barriers and facilitators to adoption, implementation, and sustainability of acupuncture treatment for older adults.

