## 1.3 Description of Intervention

The two interventions in this trial include (1) standardized acupuncture, SA, which will consist of 3 months of acupuncture therapy, with a proposed minimum of 8 treatments and a maximum of 15, and (2) enhanced acupuncture, EA, which will include the standard acupuncture plus an additional 3-month maintenance period, with a proposed minimum of 4 additional acupuncture therapy and a maximum of 6. Treatment visits will typically last 45-60 minutes. All treatments will include only acupuncture needling. Other adjunctive modalities (e.g., moxibustion or other forms of heat, cupping, gua sha, tui na), commonly used in practice, will be proscribed.

The UMC arm will consist of the care that individuals receive according to their insurance benefits plus anything else they pay for out of pocket. We will ask those assigned to UMC to avoid acupuncture for the year they are enrolled in the study. Both active treatment arms (SA, EA) will also have access to UMC as described above. Participants will be enrolled in the study for 12 months.

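### The economic analysis compares SA and EA only with UMC, so EA can look cost-effective when the added maintenance, judged against SA, is not

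*SAP*

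**What the plan says.** Aim 2, in Section 1.1 of the SAP, is "To conduct a cost-effectiveness analysis of enhanced acupuncture and standard acupuncture compared to usual care". Section 18 follows it: "We will conduct full economic evaluations (cost-utility and cost-effectiveness analyses) of SA and EA compared to UMC". The calculation paragraph there begins "We will aggregate and calculate the incremental average cost per participant in each treatment arm (SA and EA) compared to UMC". It writes out two cost differences, SA minus UMC and EA minus UMC, and sets them against the matching QALY gains and RMDQ responders. Section 9.6 of the protocol defines dominance in the same terms ("If costs of either of the acupuncture arms compared to UMC are reduced and effectiveness increased"). Both documents compare the resulting ratios with $50,000 to $100,000 per QALY. Bootstrap intervals are planned in both; the SAP adds cost-effectiveness planes and acceptability curves, without saying whether the curves are pairwise or cover all three arms.

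Section 1.3 of the SAP describes EA as the arm "which will include the standard acupuncture plus an additional 3-month maintenance period", with a proposed minimum of 4 and a maximum of 6 extra sessions. The effectiveness analysis (SAP Sections 13.1 and 13.2) does compare EA with SA. The economic analysis has no counterpart.

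**The concern.** UMC, SA and EA are mutually exclusive options, and EA contains SA. Measured only against UMC, EA is credited with everything SA achieves as well as what maintenance adds. A good SA result can therefore carry EA past the threshold even if the extra sessions buy little or nothing. The plan's own hypothesis makes this a realistic setting: EA is expected to be superior to SA, but not by a clinically important amount, while it adds paid sessions.

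Section 3 of the protocol says the design will assess the value of "maintenance acupuncture (up to 6 additional treatment sessions over months 4-6) for improving outcomes", and Section 2.2 says the evidence is meant to inform Medicare. A payer deciding whether to cover maintenance on top of a standard course would find no planned economic answer to that question.

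**Working it through.** The plan states no figure for an EA versus SA economic contrast, so there is none to reproduce. The check is algebra plus an illustration.

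**Inputs from the documents.** SA 8 to 15 sessions and maintenance 4 to 6 sessions (SAP 1.3); thresholds L = $50,000 and $100,000 per QALY (SAP 18); recruitment targets KPNC 288, KPWA 174, SH 204, IFH 123 (protocol 4.3.1.1); 20% loss (SAP 4).

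**Assumptions, not in the documents.** 12 SA and 5 maintenance sessions; price p of $60, $100 or $150 per session; SA gain over UMC G = 0.020 QALY, varied to 0.010 and 0.040; no other cost change; QALY SD 0.10 to 0.20. The maintenance gain is g.

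**Algebra.** Net benefit is L × QALYs − cost, so NB(EA vs UMC) = NB(SA vs UMC) + NB(EA vs SA).

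- EA passes against UMC when L(G + g) ≥ 17p, that is g ≥ 17p/L − G.
- EA fails against SA when Lg < 5p, that is g < 5p/L.
- Both hold when 17p/L − G ≤ g < 5p/L. The width of this range is G − 12p/L, which is SA's net benefit divided by L. It exists only if SA itself passes.
- It includes g ≤ 0, where SA dominates EA, only if GL − 12p ≥ 5p: SA's net benefit must at least cover the maintenance cost.

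**Results for G = 0.020.**

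| p | L | SA net benefit GL − 12p | Maintenance cost 5p | Range of g (QALY) | Includes SA dominating EA |
|---|---|---|---|---|---|
| $60 | $100,000 | $1,280 | $300 | -0.0098 to 0.003 | yes |
| $60 | $50,000 | $280 | $300 | 0.0004 to 0.006 | no |
| $100 | $100,000 | $800 | $500 | -0.003 to 0.005 | yes |
| $100 | $50,000 | -$200 | $500 | none | – |
| $150 | $100,000 | $200 | $750 | 0.0055 to 0.0075 | no |
| $150 | $50,000 | -$800 | $750 | none | – |

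Over the same six cells, G = 0.010, 0.020 and 0.040 give a non-empty range in 1, 4 and 6 cells, and a range including dominance in 0, 2 and 5.

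**The same point as ratios.** At the maximum sessions (15 and 21) and $100 each, costs are $1,500 and $2,100. With assumed gains over UMC of 0.040 and 0.044 QALY:

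- SA vs UMC: 1,500/0.040 = $37,500 per QALY.
- EA vs UMC: 2,100/0.044 = $47,727 per QALY, which passes at $50,000.
- EA vs SA: 600/0.004 = $150,000 per QALY, which fails at both thresholds.

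**What a reader could recover.** Subtracting the two UMC contrasts gives the EA versus SA point estimate, if the same participants and baseline adjustment are used. The interval needs their covariance. With equal arms of n and equal variances, the correct standard error is √2 × SD/√n. Treating the two contrasts as independent gives √(2 + 2) × SD/√n, which is 2/√2 = 1.41 times too large.

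**Precision of EA versus SA** (95% half-width 1.96 × SD × √(2/n), for SD 0.10 and 0.20).

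- Kaiser plus Sutter: 288 + 174 + 204 = 666; n = 666/3 × 0.8 = 177.6; 0.0208 and 0.0416 QALY.
- Kaiser only: 288 + 174 = 462; n = 462/3 × 0.8 = 123.2; 0.0250 and 0.0499 QALY.
- All four sites: 789/3 × 0.8 = 210.4; 0.0191 and 0.0382 QALY.

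Several bases are shown because the documents differ on who is included. On the full analyses, SAP 18 says "These full analyses will be conducted for the Kaiser Permanente and Sutter Health clinical sites". Protocol 6.2.2 (Aim 2 measures) says "we will only calculate the health care sector perspective for participants in the Kaiser systems". The protocol does not limit its Medicare perspective in that way and hopes for Medicare data on IFH participants.

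**The case against.** The strongest reply is that this is declared scope. Every statement of Aim 2 takes UMC as comparator, and Section 18 of the SAP matches it. The protocol's remarks on the value of maintenance concern clinical outcomes, and that EA versus SA test is planned. If EA and SA do not differ at 6 months, Section 13.1 of the SAP already commits to saying that maintenance was not shown to work, and a payer would read the EA versus UMC ratio beside that statement. Point estimates follow by subtraction, and wrongly assuming independence only widens the interval. The illustration rests on assumed inputs and on session costs alone, whereas the base case is total utilization. The added contrast would probably not settle the matter: the smallest half-width for the SAP's sites, 0.0208 QALY, is about 2.8 times the largest upper limit found at $100,000 per QALY (0.0075).

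Much of this stands. The plan is consistent with Aim 2, no stated figure is wrong, and the size is hypothetical. It does not remove the gap. The 6-month clinical conclusion concerns RMDQ, not costs and QALYs over 12 months, and is not an economic test. Under equal variances the planned UMC contrasts are about as imprecise, so imprecision is no reason to omit EA versus SA alone. A wide interval would tell a payer that the value of maintenance is unproven, which a favorable EA versus UMC ratio does not show.

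**Conclusion.** The concern holds. Neither document plans an EA versus SA cost, ratio, net benefit or ranking of the three options. The algebra is general: if SA passes against UMC, there is always a band of maintenance gains, as wide as SA's net benefit expressed in QALYs, in which EA passes against UMC and fails against SA. If SA fails, there is no such band. How likely the trial is to land in it cannot be judged from the documents; the number of affected cells depends strongly on the assumed SA gain. What the plan lacks is the joint interval, a specified three-option acceptability curve and a planned statement on EA versus SA. The consequence is confined to Aim 2. A finding that EA is cost-effective against UMC could be true, and the clinical conclusions are untouched. The change should be made, but nothing in the primary analysis depends on it.

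**What to change.** In Section 18 of the SAP and Section 9.6 of the protocol, keep both comparisons with UMC and add a full incremental analysis:

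- Order UMC, SA and EA by mean cost, and remove dominated and extendedly dominated options.
- Report EA versus SA as incremental net monetary benefit at $50,000 and $100,000 per QALY with bootstrap intervals. A ratio may be unstable if the QALY difference spans zero.
- Draw acceptability curves for all three options from the same bootstrap samples.

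This costs a few lines of text and code and needs no new data. Specifying it before unblinding avoids a choice of comparator that depends on the results. The price is a contrast that may be inconclusive: at $100,000 per QALY, under the SDs assumed above and before cost variation, the half-width is about $2,100 to $4,200 for Kaiser plus Sutter and $2,500 to $5,000 for Kaiser only. The text should say so in advance, and should state which sites enter each perspective.
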